3 INVESTIGATIONAL PLAN

3.1 Overall Study Design and Plan Description

This is a Phase IIb, randomized, double-blind, placebo-controlled, multiple dose, parallel group study. A flow chart illustrating the key components of the study is provided in Figure 1.

Figure 1 Study Flow Chart

The study comprises seven visits: Pre-screening (Visit 0), Screening (Visit 1) and then a Treatment Period consisting of Randomization (Visit 2), and weekly visits for 4 weeks (Visit 3 to Visit 6):

The Pre-screening visit (Visit 0) will be conducted for the patient to sign the informed consent, receive a patient identification number and commence washout of prohibited medications. Patients

will be dispensed rescue medication to be used as needed for increased pulmonary symptoms during the Screening, Run-in and Treatment Period.

At Visit 1, screening procedures will be performed following at least a 48-hour washout of all long-acting bronchodilators, and patients will be assessed for reversibility to albuterol.

Eligible patients will then enter a 14-day Run-in, taking open-label tiotropium as Spiriva® Respimat® once daily in the morning starting the day after Visit 1, and dispensed an electronic diary (e-diary) for recording daily symptoms and activity, rescue medication use and confirming administration of tiotropium during run-in.

Patients will then enter the Treatment Period lasting 4 weeks. At Visit 2, patients will be re-assessed for eligibility according to the randomization criteria. Eligible patients will be stratified based on reversibility to albuterol as determined at Screening (“reversible” defined as $\geq 12\%$ and ≥ 200 mL increase in FEV₁, and “non-reversible” defined as $\leq 12\%$ or < 200 mL). Each reversibility stratum will be capped at 50%. Patients will then be randomized equally across the five possible treatment arms (four doses of RPL554 and placebo) within each reversibility stratum. Following randomization, patients will do the following:

- 1) Be dispensed twice daily nebulized study medication
- 2) Take their tiotropium dose followed within 2 minutes by double-blind study medication (see Section 5.3)
- 3) Undergo serial spirometry and other assessments over 12 hours
- 4) Be instructed by unblinded study staff in the use of the nebulizer, and demonstrate their ability when taking their second dose
- 5) Take the second (evening) dose of study treatment prior to clinic discharge

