4.2 Exclusion Criteria

1. A history of life-threatening COPD including Intensive Care Unit admission and/or requiring intubation.
2. COPD exacerbation requiring oral or parenteral steroids, or lower respiratory tract infection requiring antibiotics, within 3 months of Screening or prior to the first treatment.
3. A history of one or more hospitalizations for COPD or pneumonia within 6 months of Screening or prior to the first treatment.
4. Intolerance or hypersensitivity to albuterol, tiotropium or other muscarinic receptor antagonists.
5. Other respiratory disorders: Patients with a current diagnosis of asthma, active tuberculosis, lung cancer, bronchiectasis, sarcoidosis, lung fibrosis, interstitial lung diseases, uncontrolled or unstable sleep apnea, known alpha-1 antitrypsin deficiency, cor pulmonale, clinically significant pulmonary hypertension or other active pulmonary diseases.
6. Previous lung resection or lung reduction surgery.
7. Pulmonary rehabilitation, unless such treatment has been stable from 4 weeks prior to Screening and remains stable during the study.
8. Oral therapies for COPD (e.g. oral steroids, theophylline, and roflumilast) or antibiotics within 3 months prior to Screening, or ICS therapy within 4 weeks prior to Screening (additional prohibited medications, with shorter washout periods than those above, are shown in Table 3.)
9. Prior exposure to RPL554.
10. History of, or reason to believe a patient has, drug or alcohol abuse within the past 5 years.
11. Received an experimental drug within 30 days or five half-lives, whichever is longer.
12. Women who are pregnant or breast-feeding.
13. Patients with uncontrolled disease including, but not limited to, endocrine, active hyperthyroidism, neurological, hepatic, gastrointestinal, renal, hematological, urological, immunological, psychiatric, or ophthalmic diseases that the Investigator believes are clinically significant. This includes any hepatic disease or moderate to severe renal impairment.
14. Patients with historical or current evidence of clinically significant cardiovascular disease. Significant is defined as any disease that in the opinion of the investigator would put the safety of the subject at risk through participation or which could affect the efficacy or safety analysis if the disease/condition were to exacerbate during the study. In particular, the following are excluded:
 - Myocardial infarction or unstable angina within 6 months prior to Screening

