5.9 Prior and Concomitant Therapies and Medications

5.9.1 Prior and Concomitant COPD Medications

All prior therapies for COPD taken in the 3 months prior to Visit 1 and all concomitant COPD therapies will be recorded in the eCRF, with the medication, dose, route and start and stop date(s)

and time(s) clearly recorded to document all required washout periods and compliance with the Inclusion and Exclusion Criteria.

Tiotropium use at a stable dose once daily will be administered during the Run-in and Treatment Periods, starting on the morning after Visit 1.

Upon providing informed consent, patients will discontinue COPD medications for the time periods described in Table 3 prior to the Screening visit and will remain off these medications for the duration of the study.

Table 3 Restrictions for COPD Medications Prior to Screening

Medication	Time Interval Prior to Screening Visit
Oral COPD therapies – e.g. oral steroids, theophylline, roflumilast (Oral mucolytics allowed)	3 months
Antibiotics	3 months
Terbutaline	1 day
Short-acting antimuscarinics (e.g., ipratropium)	1 day
Once or twice daily bronchodilators (LAMA, LABA or LAMA/LABA)	48 hours
Inhaled corticosteroids	4 weeks
Nebulized therapies (other than study medication)	1 week if a bronchodilator 4 weeks if an ICS

Abbreviations: COPD=chronic obstructive pulmonary disease; ICS=inhaled corticosteroids; LABA: long acting β 2 agonist; LAMA=long acting muscarinic antagonist

The following therapies are subject to restriction as indicated:

- Patients must continue to take their background tiotropium medication at the same dose and regimen throughout the Run-in and Treatment Periods. Starting or stopping tiotropium or changes in dosing is not allowed.
- Albuterol may be used as a rescue medication (see Section 5.10), but must be withheld for at least 6 hours prior to spirometry (per below), and this is to be confirmed in the spirometry system. If this withhold is not met, the patient should be rescheduled for a repeat visit within permitted windows. Short acting bronchodilators should be withheld as follows:
 - 6 hours prior to pre-reversibility spirometry at Visit 1 for Screening
 - 6 hours prior to pre-dose spirometry for all subsequent visits
 - Until the completion of all spirometry assessments for all visits

If following the above requirements provide inadequate symptom control, patients should contact the Investigator.

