6 STUDY PROCEDURES AT EACH VISIT

The study will consist of seven visits:

- Pre-Screening (Visit 0), occurring between 2 and 28 days before Visit 1 (sufficient to allow for washout of prohibited medications)
- Screening (Visit 1), occurring 14 (± 1) days prior to the first study treatment administration. Screening procedures ideally should occur over the course of a single day, but may be done over more than one day if necessary. All Screening procedures must be performed prior to initiation of the run-in (i.e., administration of open-label tiotropium)
- Five treatment visits (Visit 2 to Visit 6) each separated by 7 (± 1) days

The schedule of assessments at each visit is shown in Table 4 and listed in Section 6.1 to Section 6.6. The study assessments are described in Section 7.

Post-dose assessments generally should be performed in the following order (as applicable): 1) 12-lead ECG, 2) vital signs, 3) PK blood sample, 4) spirometry.

Table 4 Schedule of Assessments

Visit	Visit 0 Pre-Screen	Visit 1 Screening (Week -2 ±1 d)	Visit 2 Randomiza- tion	Visit 3 (Week 1 ±1 d)	Visit 4 (Week 2 ±1 d)	Visit 5 (Week 3 ±1 d)	Visit 6 End of Study (Week 4 ±1 d or ET)	Telephone Follow-up (1 week after Visit 6 ±2 d)
Informed consent	X							
Assign patient number	X							
Dispense albuterol^(a)	X							
Prohibited medication washout	X							
Demographics		X						
Medical/surgical & disease history		X						
Inclusion/exclusion criteria		X	X					
Randomization criteria			X					
Prior/concomitant medications/therapies		X	X	X	X	X	X	
Physical examination		X						X
Height and body weight		X						X ^(b)
mMRC questionnaire		X	X					
12-lead ECG (QTcF and heart rate)		X	X ^(c)	X ^(c)				X ^(c)
Vital signs (blood pressure, pulse)		X	X ^(d)	X ^(e)	X ^(e)	X ^(e)		X ^(d)
Laboratory safety tests		X						X
Urinalysis		X						X
Viral serology		X						
Pregnancy test^(f)		X	X					X
Reversibility test		X						
Chest X-ray (if needed)		X						
Adverse event questioning		X	X	X	X	X	X	X
Slow spirometry (inspiratory capacity) - 30 min & +2 hours^(g)			X					X
Forced spirometry -30 min to +12 hours^(h)			X					X
Forced spirometry -30 min to +3 hours⁽ⁱ⁾				X	X	X		

Visit	Visit 0 Pre-Screen	Visit 1 Screening (Week -2 ±1 d)	Visit 2 Randomiza- tion	Visit 3 (Week 1 ±1 d)	Visit 4 (Week 2 ±1 d)	Visit 5 (Week 3 ±1 d)	Visit 6 End of Study (Week 4 ±1 d or ET)	Telephone Follow-up (1 week after Visit 6 ±2 d)
Dispense tiotropium		X	X					
Dispense symptom e-diary		X						

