6.2 Visit 0 (Pre-screening)

The following will be performed at the Pre-screening visit:

- Obtain written informed consent (see Section 10.3)
- Assign patient identification number (see Section 5.7)
- Dispense rescue albuterol and instruct patient to wash out of prohibited medications
- Instruct patient to return 2 to 28 days later (as required for medication washout) for Visit 1

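### Stop-on-consent in Section 5.9.1 covers the 3-month rows of Table 3, which the 2 to 28 day window before Screening cannot hold; those rows should be labelled as look-back exclusions

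*Protocol*

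**What the plan says.** Protocol Section 5.9.1 sets the rule: "Upon providing informed consent, patients will discontinue COPD medications for the time periods described in Table 3 prior to the Screening visit". Patients then stay off these drugs for the rest of the study. Table 3 has seven rows. Two carry a 3-month interval (oral COPD therapies such as oral steroids, theophylline and roflumilast; antibiotics), and the other five run from 1 day to 4 weeks.

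Washout starts at Visit 0. Section 3.1 has the patient sign consent there, "receive a patient identification number and commence washout of prohibited medications", and the Synopsis places consent before any study procedure, including washout. Section 6 describes Visit 0 as "occurring between 2 and 28 days before Visit 1 (sufficient to allow for washout of prohibited medications". Section 6.2 gives the site two instructions: "Dispense rescue albuterol and instruct patient to wash out of prohibited medications" and "Instruct patient to return 2 to 28 days later (as required for medication washout) for Visit 1".

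Eligibility is judged at Visit 1. Exclusion 8 in Section 4.2 rules out "Oral therapies for COPD (e.g. oral steroids, theophylline, and roflumilast) or antibiotics within 3 months prior to Screening", and the same criterion rules out inhaled corticosteroid (ICS) within 4 weeks. It then adds that "additional prohibited medications, with shorter washout periods than those above, are shown in Table 3". Inclusion 13 requires the Section 5.9.1 intervals to be met. Table 4 places the washout at Visit 0, but first schedules the prior-medication review and the inclusion/exclusion check at Visit 1.

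**The concern.** One instruction and one time window are applied to two different kinds of restriction. An ICS or a long-acting bronchodilator can be stopped at consent and be out of the way by Visit 1. An oral COPD drug still in use at consent cannot meet a 3-month interval by Visit 1, whichever permitted day is chosen. The statement that the window is sufficient is therefore wrong for two rows.

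What is at stake is the care of a patient on maintenance oral treatment. If a site reads Section 5.9.1 literally, the drug is stopped at Visit 0 although the patient cannot pass Exclusion 8 or Inclusion 13 at that Screening. The patient bears the risk of withdrawal, the site carries an avoidable screen failure, and the trial gains nothing. Section 5.11 mentions resuming usual COPD therapy only at the end of treatment, and Section 4.4.1 does not say what a screen failure should do about a stopped drug. Nothing forbids resumption, but nothing prompts it.

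**Working it through.** **Inputs.** Window from Visit 0 to Visit 1: minimum 2 days, maximum 28 (Sections 6 and 6.2). Intervals: Table 3. The documents do not convert 3 months to days. Counted on the calendar back from every possible Screening date in the planned period (May to November 2019), 3 months is 89 to 92 days.

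**Formula.** Days to spare = 28 − interval. A negative result means that the interval cannot be completed even at the latest permitted Visit 1.

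| Table 3 row | Interval (days) | 28 − interval |
|---|---|---|
| Oral COPD therapies | 89 to 92 | −61 to −64 |
| Antibiotics | 89 to 92 | −61 to −64 |
| Terbutaline | 1 | 27 |
| Short-acting antimuscarinics | 1 | 27 |
| Once or twice daily bronchodilators | 2 | 26 |
| ICS | 28 | 0 |
| Nebulized therapies | 7 (bronchodilator) or 28 (ICS) | 21 or 0 |

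So the sufficiency statement in Section 6 holds for 5 of 7 rows and fails for 2 of 7. The 28-day cap equals the longest of the five intervals that fit, which suggests that the window was set with those rows in mind.

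**Sensitivity.** With 3 months taken as 90 days, the gap is 90 − 28 = 62 days. With 12 weeks it is 84 − 28 = 56 days. At the earliest permitted Visit 1 it is 89 − 2 = 87 to 92 − 2 = 90 days. No reading closes it. Section 3.3 gives 83 days as the longest planned participation per patient, which is itself shorter than 89.

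**Consequence at Screening.** A patient who stops an oral COPD drug on day 0 is at most 28 days off it at Visit 1, so Exclusion 8 is met and Inclusion 13 is not. The earliest Screening that could be passed is day 89 to 92. That would need a re-screening, and the patient would have to stay off the drug until then.

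**Order of steps.** Section 6.2 lists consent, patient number, rescue albuterol with the washout instruction, and the return date. It lists no review of current drugs or of eligibility before the instruction, and Table 4 agrees. Section 8.2 expects medical notes to be updated with concomitant medication after each visit, but that is documentation and does not hold back the washout.

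**The case against.** The strongest reply is that the protocol already treats 3 months as a look-back. Exclusion 8 is keyed to past use. Section 5.9.1 opens by having the site record COPD therapies over the 3 months before Visit 1, which necessarily reaches back before consent, and it does so partly to document eligibility. Table 3 is headed as restrictions, with intervals counted back from Screening. On this reading a current theophylline or roflumilast user is excluded and is never a candidate for washout. Moreover, to set the return date under Section 6.2 the site has to match the patient's drugs to Table 3, and for an oral COPD drug it would find that no permitted date exists.

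Much of this stands. The look-back is the likely intent, and an attentive site would probably not stop the drug. A reader might infer from the text that every such patient is certain to be taken off treatment and then to fail; the documents do not support that, because the site may notice the conflict first.

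The reply does not settle the matter, however. Exclusion 8 puts the 3-month interval alongside the 4-week ICS interval, which is washed out after consent. Meeting Exclusion 8 on the day of consent therefore does not tell a site to leave the drug alone. The criterion's own closing words treat the intervals before them as washout periods, although this is modest evidence because the ICS interval is among them. The 3-month medication record is first scheduled at Visit 1, after the instruction to stop. With approximately 50 centers planned, the exception should be written down and not left to each site to infer.

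The affected group is also narrower than two rows suggest. Exclusion 2 already removes many short-course users on history ("COPD exacerbation requiring oral or parenteral steroids, or lower respiratory tract infection requiring antibiotics, within 3 months of Screening"), so the practical concern is maintenance oral therapy. Further mitigations are rescue albuterol from Visit 0, the instruction to contact the Investigator if symptoms are poorly controlled, adverse event recording from consent, and possible re-screening in consultation with the Medical Monitor. These soften the harm of an unnecessary withdrawal but do not prevent it.

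**Conclusion.** The point holds as a minor patient-safety and screen-failure issue. Section 5.9.1 applies stop-on-consent to all of Table 3, and the sufficiency statement in Section 6 is untrue for the two 3-month rows. A literal reading could withdraw maintenance oral therapy from a patient who has no route to passing that Screening.

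Two stronger inferences should be resisted. The gap of 61 to 64 days shows that the window and the interval are incompatible; it does not measure harm, since a 3-month washout was probably never intended. Nor does the issue reach the results: it concerns patients who fail Screening and are not randomized, so the efficacy analysis is unaffected.

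The conclusion assumes that 3 months means calendar months, though 12 weeks would give the same answer. It also assumes that some patients are on maintenance oral COPD therapy when they consent. The documents do not say how many, so the size of the harm cannot be stated.

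**What to change.** - In Section 5.9.1, Table 3 and Section 6, limit stop-on-consent and the statement about sufficient washout time to intervals of 4 weeks or less.
- In the same places, state that the 3-month rows are look-back exclusions and that no such drug is to be stopped in order to qualify.
- In Section 6.2 and Table 4, add a check of current COPD drugs and last-use dates at Visit 0, before the washout instruction.

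No interval, eligibility threshold or analysis changes. The cost is a few sentences, a few more minutes at Visit 0, and a re-confirmation at Visit 1 because the look-back is counted from Screening.

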6 STUDY PROCEDURES AT EACH VISIT

The study will consist of seven visits:

- Pre-Screening (Visit 0), occurring between 2 and 28 days before Visit 1 (sufficient to allow for washout of prohibited medications)
- Screening (Visit 1), occurring 14 (± 1) days prior to the first study treatment administration. Screening procedures ideally should occur over the course of a single day, but may be done over more than one day if necessary. All Screening procedures must be performed prior to initiation of the run-in (i.e., administration of open-label tiotropium)
- Five treatment visits (Visit 2 to Visit 6) each separated by 7 (± 1) days

The schedule of assessments at each visit is shown in Table 4 and listed in Section 6.1 to Section 6.6. The study assessments are described in Section 7.

Post-dose assessments generally should be performed in the following order (as applicable): 1) 12-lead ECG, 2) vital signs, 3) PK blood sample, 4) spirometry.

Table 4 Schedule of Assessments

Visit	Visit 0 Pre-Screen	Visit 1 Screening (Week -2 ±1 d)	Visit 2 Randomiza- tion	Visit 3 (Week 1 ±1 d)	Visit 4 (Week 2 ±1 d)	Visit 5 (Week 3 ±1 d)	Visit 6 End of Study (Week 4 ±1 d or ET)	Telephone Follow-up (1 week after Visit 6 ±2 d)
Informed consent	X							
Assign patient number	X							
Dispense albuterol^(a)	X							
Prohibited medication washout	X							
Demographics		X						
Medical/surgical & disease history		X						
Inclusion/exclusion criteria		X	X					
Randomization criteria			X					
Prior/concomitant medications/therapies		X	X	X	X	X	X	
Physical examination		X						X
Height and body weight		X						X ^(b)
mMRC questionnaire		X	X					
12-lead ECG (QTcF and heart rate)		X	X ^(c)	X ^(c)				X ^(c)
Vital signs (blood pressure, pulse)		X	X ^(d)	X ^(e)	X ^(e)	X ^(e)		X ^(d)
Laboratory safety tests		X						X
Urinalysis		X						X
Viral serology		X						
Pregnancy test^(f)		X	X					X
Reversibility test		X						
Chest X-ray (if needed)		X						
Adverse event questioning		X	X	X	X	X	X	X
Slow spirometry (inspiratory capacity) - 30 min & +2 hours^(g)			X					X
Forced spirometry -30 min to +12 hours^(h)			X					X
Forced spirometry -30 min to +3 hours⁽ⁱ⁾				X	X	X		

Visit	Visit 0 Pre-Screen	Visit 1 Screening (Week -2 ±1 d)	Visit 2 Randomiza- tion	Visit 3 (Week 1 ±1 d)	Visit 4 (Week 2 ±1 d)	Visit 5 (Week 3 ±1 d)	Visit 6 End of Study (Week 4 ±1 d or ET)	Telephone Follow-up (1 week after Visit 6 ±2 d)
Dispense tiotropium		X	X					
Dispense symptom e-diary		X						
Review symptom e-diary			X	X	X	X	X	
SGRQ-C, BDI/TDI & CAT questionnaires			X		X		X	
Pre-dose PK blood sample ⁽ⁱ⁾			X		X			
Randomization			X					
Administer study treatments (tiotropium & double-blind study medication) ^(k)			X ^(l)	X	X	X	X	
Nebulization inhalation training			X					
Dispense study medication & nebulizer			X	X	X	X		
Dispense compressor			X					
Collect study medication & nebulizer				X	X	X	X	
Study treatment compliance (including tiotropium)			X	X	X	X	X	
Administer PGAC questionnaire					X		X	
Collect compressor							X	
Collect symptom e-diary								X

Abbreviations: BDI/TDI=Baseline Dyspnea Index/Transition Dyspnea Index; CAT=COPD assessment test; d=days; ECG=electrocardiogram; ET=early termination; mins=minutes; mMRC=modified Medical Research Council; QTcF=QT interval corrected using Fridericia's formula; PGAC=Patient Global Assessment of Change; PK=pharmacokinetics; SGRQ-C=St George's Respiratory Questionnaire-COPD specific

- (a) A second canister of albuterol may be dispensed during the study if necessary
- (b) Body weight only at Visit 6
- (c) ECG at Visits 2, 3 and 6 is performed pre-dose and 2 hours post-dose
- (d) Vital signs at Visits 2 and 6 are measured pre-dose and 30 minutes, 1, 2, 4, 6, 8 and 12 hours post-dose
- (e) Vital signs at Visits 3, 4 and 5 are measured pre-dose and 30 minutes, 1, 2 and 3 hours post-dose
- (f) Serum pregnancy test at Visit 1; urine pregnancy test at Visits 1, 2 and 6
- (g) Inspiratory capacity is performed via slow maneuver prior to forced efforts at Visits 2 and 6, 30 minutes pre-dose and 2 hours post-dose.
- (h) Forced efforts at Visits 2 and 6 are performed 30 minutes pre-dose (after inspiratory capacity), followed by 30 minutes and 1, 2, 3, 4, 6, 8 and 12 hours post-dose
- (i) Spirometry at Visits 3, 4 and 5 is performed 30 minutes pre-dose, followed by 30 minutes and 1, 2 and 3 hours post-dose

Visit	Visit 0 Pre-Screen	Visit 1 Screening (Week -2 ±1 d)	Visit 2 Randomiza- tion	Visit 3 (Week 1 ±1 d)	Visit 4 (Week 2 ±1 d)	Visit 5 (Week 3 ±1 d)	Visit 6 End of Study (Week 4 ±1 d or ET)	Telephone Follow-up (1 week after Visit 6 ±2 d)

(j) Pre-dose samples are for assay of tiotropium steady state exposure prior to and following 14 days of treatment with RPL554. PK samples from Visit 4 will also be used for assay pf RPL554 concentrations
 
(k) Study medication is to be dosed following administration of tiotropium
 
(l) At Visit 2, study medication is to be administered twice; first, just after randomization and again 12 hours later once all assessments are complete
								

